After mechanical therapy was completed, the unmasked clinician (LK or MB) randomly assigned patients to test simvastatin in methylcellulose (SIM/MCL) or control (MCL) groups. The root surface was etched for 2 minutes with ethylenediaminetetraacetic acid (EDTA, Pref-Gel, Straumann, Andover, MA) followed by irrigation with sterile saline. SIM and MCL were prepared by local compounding pharmacy (Pharmacy Solutions Lincoln, NE) and mixed immediately prior placement to achieve 2.2 mg simvastatin (SIM) suspended in 0.15 ml methylcellulose gel (MCL) (test group) or 0.15 ml of methylcellulose gel alone (control group)(Figure 5).

Gels were placed at the base of the pocket and deposited up the interproximal root surface of the experimental tooth (Figure 6). The papilla were re-approximated under pressure and sealed using cyanacrylate (PeriAcryl, Glustitch, Delta, BC, Canada). Routine periodontal maintenance therapy (PMT) then was completed by MC or LA, including full mouth periodontal charting, debridement, and root planing of inflamed pockets avoiding the experimental area. Patients were instructed to avoid brushing and flossing of the experimental site for 6 weeks. They were dispensed Listerine (Johnson & Johnson Consumer, Inc., New Brunswick, New Jersey) and instructed to be used twice a day for 30 seconds for 6 weeks. Patients were asked to return for postoperative visits after 2 and 6 weeks along with PMT recalls at 3, 6, 9, and 12 months. GCF collection was repeated at 2- weeks and 12-month PMT visits and clinical measurements were repeated at 12 months (Figure 7) by one of the three calibrated examiners (AK, RR, and HR). Collection of approximately 2x2x2 mm interproximal tissue was repeated at 2 weeks by either LK or MB. During the 6-week follow up, patients were given Gel-Kam® preventative treatment gel (Colgate Oral Pharmaceuticals, NY, NY) and a GUM® Proxabrush® (Sunstar Americas, Inc., Schaumburg, IL) and patients were instructed to brush the experimental site twice a day using the provided

interproximal brush. Participants were questioned about adverse events at 2-weeks and 6-months, and 12-months PMT visits.

Figure 2: Baseline GCF Sample

Perioscope use

Figure 3: Baseline Interproximal tissue

Figure 4:

Figure 5: Mixing SIM & MCL

Figure 6: Placement of SIM

Figure 7: 12-months post-therapy

Analysis of GCF samples

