Each GCF sample containing two paper strips was eluted using 85 μ l of 1 \times PBS by gently agitating the samples on a rocker plate for 1 h at 4°C. Analyte concentrations were measured using magnetic bead panels (Millipore, Billerica, MA) and read on a MAGPIX with Luminex xPONENT software (Luminex Corporation, Austin, TX) per the manufacturers' recommendations.

Nine analytes were measured: Fibroblast growth factor (FGF-2), interleukin (IL)-1 β , IL-6, IL-10, IL-17A, insulin-like growth factor 1 (IGF-1), tumor necrosis factor (TNF)- α , receptor activator of nuclear factor kappa-B ligand (RANKL), and vascular endothelial growth factor A (VEGF-A). The amounts of cytokines are reported in picograms per ml, then mathematically adjusted by multiplying 0.085 to achieve pg per sample.

Analysis of interproximal tissue samples

Interproximal tissue samples were collected between the interproximal sulcus of the experimental site and adjacent tooth and were stored in 1.5 mL RNA/*later* solution (ThermoFisher Scientific, Waltham, MA). RNA extraction was conducted using the NucleoSpin RNA XS—complete kit for isolation and purification of total RNA from extremely small samples (Marcherey – Nagel, [Düren, Germany](#)). DNA digestion and cDNA synthesis were done using the QuantiTect Reverse Transcription Kit from QIAGEN© (Germantown, MD) per the manufacturers' recommendations.

Samples were diluted with water and placed in 96-well custom array plates in technical triplicate; qPCR was executed with SsoAdvanced Universal SYBR Green Supermix from Bio-Rad (Hercules, CA) reagents. PCR conditions were 39 cycles at 95°C for 3 minutes (1 cycle) 95°C for 15 seconds, and at 58°C for 30 seconds (39 cycles). At the end point of rt-PCR analysis, the threshold cycle

or $\Delta\Delta Ct$ values were recorded. To analyze the relative changes in gene expression, the $2^{\Delta\Delta Ct}$ method was done, as described by Livak et al (2001).

Statistical analyses

A sample size of 22 per group was needed to achieve at least 80% power to detect a difference of 1.0 mm in clinical attachment level between groups with a common estimated group standard deviation of 1.1 mm with a significance level of 0.05 using a two-sided two-sample t-test. This is based on mean data from most relevant previous studies (Killeen et al., 2012 and Jasa et al., 2019).

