For the experimental interproximal treatment sulcus, BOP was considered present at baseline if at least one buccal or lingual interproximal site had the condition present. The follow-up variables for BOP were determined as follows: if the patient started without BOP and ended without BOP or showed a reduction (i.e. presence of BOP at baseline to absence of BOP at 12 months), that patient was considered to have a good outcome. If the patient began with BOP and showed no improvement or they developed BOP, that patient was considered to have a poor outcome. Associations between categorical variables were assessed using Chi-Square tests, or Fisher's exact tests when expected cell counts were low. Medians and inter-quartile ranges (IQRs; the range of the middle 50% of the data (25th percentile, 75th percentile)) were calculated for each treatment condition, and Wilcoxon Rank Sum tests were used to examine differences in distributions of BOP between the two treatment conditions (i.e. SIM/MCL or MCL) for baseline BOP values. For the change in BOP outcome, logistic regression models were used, which included group and adjusted for worst side. Adjusted odds ratios are presented with 95% confidence intervals.

Descriptive statistics for raw GCF and RT-PCR continuous data are given as medians and interquartile ranges (IQRs, representing the range of the middle 50% of the data). For analysis, data was log transformed due to skew.

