General estimating equations were run with each measure of interest as the outcome, and each model included the variables (analyte) group and time, as well as the interaction between group and time to assess if change over time differed by group. If the interaction was not significant, main effects models were run. P-values for post hoc comparisons were adjusted using simulation methods. Pearson correlations were also run to assess for association between GCF and interproximal tissue samples at a given time point. Clinical attachment level (CAL) change between baseline and 12-months was the primary clinical outcome measure for this clinical trial. For change in CAL baseline CAL values were subtracted from 12 months CAL value, and difference scores were plotted against GCF and rt-PCR measures at two weeks (i.e. > negative values indicate reduction in clinical attachment loss). Associations between change in CAL and measures at 2-weeks were assessed using Pearson correlations. All analyses were performed using SAS software version 9.4 (SAS Institute Inc., Cary, NC).

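### No adjustment for treatment group is named when 12-month CAL change is correlated with 2-week markers; if arms are pooled, a treatment effect on both can create or mask a correlation

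*Combined protocol and SAP*

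**What the plan says.** The Statistical analyses section makes CAL change from baseline to 12 months the primary clinical outcome. It then relates that change to the early biological measures: "difference scores were plotted against GCF and rt-PCR measures at two weeks", and "Associations between change in CAL and measures at 2-weeks were assessed using Pearson correlations". A second set of correlations links the two specimen types: "Pearson correlations were also run to assess for association between GCF and interproximal tissue samples at a given time point". No sentence on these correlations mentions treatment arm.

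Other analyses in the same section do name it. For the estimating-equation models of the markers, "each model included the variables (analyte) group and time, as well as the interaction between group and time". For change in bleeding on probing, "logistic regression models were used, which included group and adjusted for worst side".

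The Treatment Protocol section shows that patients were "randomly assigned patients to test simvastatin in methylcellulose (SIM/MCL) or control (MCL) groups" before the gel was placed. GCF was collected again at 2 weeks and at 12 months, while collection of "interproximal tissue was repeated at 2 weeks" and at no later visit. Two weeks is therefore the only time after treatment at which both specimens exist.

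**The concern.** The 2-week marker and the 12-month CAL change both follow randomised treatment, so arm is a potential common cause of both. The trial is sized for an effect on CAL, and the marker models are built to look for an effect on the markers. If the drug does both, a scatterplot of all patients shows two shifted clouds, and a Pearson correlation across them picks up the shift even when there is no relation inside either cloud.

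Such a correlation would be read as evidence about mechanism: that patients with a given marker level at 2 weeks go on to gain more attachment. It might only restate that the drug moved both variables. The reverse is also possible. If the treatment shifts run against the within-arm relation, a real link can be cancelled. The same reasoning applies to the GCF-tissue correlations at 2 weeks. It does not apply to those at baseline, which precede treatment.

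**Working it through.** **The plan's own figure.** The sample size statement reads: "A sample size of 22 per group was needed to achieve at least 80% power to detect a difference of 1.0 mm", with SD 1.1 mm and a two-sided 0.05 t-test. The standardised CAL effect is 1.0/1.1 = 0.909. Noncentral-t power at 22 per group is 83.8%, and 21 per group is the first size clearly above 80% (82.0%; 20 gives 80.0% only after rounding). The stated 22 meets its own requirement.

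**Inputs.** From the documents: 22 per group (N = 44), CAL effect 0.909 SD, two-sided 0.05. Assumed: the 1.1 mm SD applies to CAL change; both variables are normal within arm (markers on the log scale); marker effects of 0 to 1.5 SD; within-arm correlations of 0 and 0.4.

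**Pooled correlation.** Let ρ be the within-arm correlation, d₁ the treatment effect on CAL change and d₂ that on the marker, in within-arm SDs. With equal arms, the between-arm covariance d₁d₂/4 adds to the within-arm covariance, and each variance gains d²/4:

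r(pooled) = (ρ + d₁d₂/4) / √[(1 + d₁²/4)(1 + d₂²/4)]

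Example with ρ = 0, d₁ = 0.909, d₂ = 1.0: the numerator is 0.909/4 = 0.227, the denominator √(1.207 × 1.25) = 1.228, so r = 0.185. A true within-arm correlation of zero appears as 0.19. The critical |r| at N = 44 is 0.297.

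**Rejection rates.** 100,000 simulated trials per setting, comparing the pooled Pearson test (42 df) with the partial correlation given group (41 df).

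*No within-arm link (ρ = 0), planned CAL effect:*

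| Marker effect (SD) | Pooled r | Pooled test rejects | Given group |
|---|---|---|---|
| 0 | 0 | 5% | 5% |
| 0.2 | 0.04 | 6% | 5% |
| 0.3 | 0.06 | 7% | 5% |
| 0.5 | 0.10 | 10% | 5% |
| 0.8 | 0.15 | 17% | 5% |
| 1.0 | 0.19 | 23% | 5% |
| 1.5 | 0.25 | 39% | 5% |

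With half the planned CAL effect (0.455 SD), the pooled rates are 6%, 8%, 10% and 14% at marker effects of 0.5, 0.8, 1.0 and 1.5 SD. With no CAL effect, the rate is 5% at every marker effect.

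*Masking (ρ = 0.4, planned CAL effect, marker shift opposing the within-arm link):*

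| Marker effect (SD) | Pooled r | Pooled power | Given group |
|---|---|---|---|
| 0.3 | 0.30 | 51% | 77% |
| 0.5 | 0.25 | 37% | 77% |
| 0.8 | 0.18 | 20% | 77% |
| 1.0 | 0.14 | 13% | 77% |

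When the shifts run with the link, pooled power rises instead: 83%, 89% and 94% at 0.3, 0.5 and 0.8 SD. That gain comes from the treatment shift, not from better detection of the within-arm relation.

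The formula holds for any two post-treatment variables, so it also covers a GCF analyte and a tissue transcript at 2 weeks. The documents give no effect size for either, and the planned CAL effect plays no part there.

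**The case against.** The strongest reply concerns the target. The plan speaks only of associations and claims no within-arm prediction, mediation or surrogacy. For the marginal association, a pooled Pearson correlation answers the question, and a non-zero value caused by treatment is not a false positive. This stands as a matter of definition: the rates above are error and power rates for the within-arm association only. But the between-arm effects on markers are already addressed by models with a group term. What a correlation could add is the within-arm link, and the pooled version cannot separate it from the treatment effect.

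Pooling is also inferred. Separate correlations by arm, or plots marked by arm, would fit the same sentences. This stands too, and is why the conclusion is conditional. Still, a Pearson correlation has no place for a third variable, and the section names group where it is used.

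Finally, the distortion is small in moderate settings: with both treatment effects at 0.5 SD the pooled test rejects in about 7% of trials, and at 0.3 SD in about 5%. The large figures need the full planned CAL benefit and a marker shift of 0.8 SD or more. That limits the importance of the point but does not remove it, because the full CAL benefit is what the trial was sized to detect.

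**Conclusion.** The concern holds, conditionally on pooling, as an improvement worth considering and not a threat to the trial. The stated analysis names no group adjustment. If the arms are pooled and treatment affects both variables, a nominal 5% test of the within-arm association can reject in anything from barely more than 5% to about 39% of trials over the assumed range of marker effects, and opposing shifts can cut power from about 77% to 13%.

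The size rests on assumed marker effects and within-arm correlations, and on applying the planning SD to CAL change. If treatment moves only one variable, there is no inflation. The extension to the 2-week GCF-tissue correlations follows by the same argument, but its size cannot be judged from the documents. The between-group CAL comparison and the sample size are unaffected.

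**What to change.** - State whether the arms were pooled in each set of correlations.
- Base the marker-CAL association on a partial correlation given group, or on a linear model of CAL change (or 12-month CAL) on the log 2-week marker and group. Baseline CAL is an inexpensive optional covariate; it does not itself address the group problem.
- Partial out group in the 2-week GCF-tissue correlations.
- Identify the arms in the plots.
- Show any unadjusted correlation alongside, as descriptive.
- The Patient Population section says the trial ended in December 2020, so label the adjusted analysis as added afterwards if results have already been seen.

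The cost is a few lines of code on data already held and one or two degrees of freedom per model. Some unadjusted correlations may lose significance.
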